## 13. ASSESSMENT OF SAFETY

Safety will be assessed by the frequency and severity of adverse events (AE).

### 13.1. Specifications of Safety Parameters

#### 13.1.1. ***Definition of Adverse Events (AE)***

Adverse events (AEs) will be recorded at administration of the treatment and during phone calls once the patient is discharged, in the study patient record (source document) as well as on a specific AE case report form (CRF).

An AE is any untoward medical occurrence in a study patient or clinical investigation participant administered a pharmaceutical product. An AE does not necessarily have a causal relationship with this treatment. An AE can therefore be any unfavorable and unintended sign, symptom, or disease temporally associated with the use of a medicinal product, whether or not related to the medicinal product, e.g.:

- any new clinical diagnosis
- any symptom that requires medical clarification or leads to in-patient admission (surgery or accident)
- any suspected adverse drug reaction (ADR)
- any symptom, such as fever, that appears on the study patient's medical records
- any event related in time with the application of the study medication and affecting the health of the study patient (including laboratory value changes)

For the purposes of this study, baseline symptoms will be collected prior to the administration of study intervention. Only those symptoms identified as new or worsened compared to the baseline assessment will be recorded as an AE. In addition, only those abnormal laboratory values or physical examination assessments that are considered clinically significant will be recorded in the study documents.

If there is any doubt as to whether a clinical observation is an AE, the event will be recorded and assessed by the study medical monitor. AEs must be graded for severity and relationship to study product. Adverse events of special interest (AESI) will be defined as newly acquired transmissible infectious diseases.

#### 13.1.2. ***Definition of Serious Adverse Events (SAE)***

An adverse event or suspected adverse reaction is considered "serious" if, in the view of the PI, it results in any of the following outcomes:

- Death
- Life-threatening adverse event\*
- Inpatient hospitalization or prolongation of existing hospitalization
  - Subjects might be admitted to an inpatient unit to be eligible for the study; in these cases the initial hospitalization will not be considered an SAE in and of itself, rather it will only be considered an SAE if the planned hospitalization is prolonged
- A congenital anomaly/birth defect

- Persistent or significant disability or incapacity or substantial disruption of the ability to conduct normal life function
- Important medical events that may not result in death, be life-threatening, or require hospitalization may be considered when, based upon appropriate medical judgement, they may jeopardize the patient or subject and may require medical or surgical intervention to prevent one of the outcomes listed in this definition

\*Life-threatening adverse event. An adverse event is considered “life-threatening” if, in the view of the PI, its occurrence places the patient or participant at immediate risk of death. It does not include an adverse event which, had it occurred in a more severe form, might have caused death.

Any adverse event or suspected adverse reaction that meets the criteria for serious adverse event will be:

- recorded on the appropriate SAE CRF
- followed through resolution by a study clinician or up to 30 days post-treatment, whichever comes first
- reviewed and evaluated by a study clinician

### **13.1.3. *Definition of Unanticipated Problems (UP)***

On enrollment in the study, the study participants will be instructed to contact the medical monitor if an AE occurs. Patients will be given a patient diary with date, details and action taken to help with data collection. This diary will be taken to the site PI for evaluation if needed and patients instructed to seek immediate medical attention if indicated.

## **13.2. Classification of an Adverse Event**

### **13.2.1. *NIH Grading of Severity of Events***

AEs will be assessed by the clinician using the NIH Common Terminology Criteria for Adverse Events (CTCAE) defined grading system (Appendix 17.3). Briefly, the criteria for estimating adverse event severity grade:

- **Grade 1, Mild:** Asymptomatic or mild symptoms; clinical or diagnostic observations only; intervention not indicated.
- **Grade 2, Moderate:** Minimal, local or noninvasive intervention indicated; limiting age-appropriate instrumental activities of daily living (ADL).
- **Grade 3, Severe:** Severe or medically significant but not immediately life-threatening; hospitalization or prolongation of hospitalization indicated; disabling; limiting self-care ADL.
- **Grade 4, Life threatening:** Places the patient or subject at immediate risk of death. It does not include an adverse event that, had it occurred in a more severe form, might have caused death.
- **Grade 5, Death**

### **13.2.2. *Relationship to Study Agent***

All adverse events, regardless of relatedness, should be reported. All adverse events should be evaluated for relatedness when reporting and documenting on the CRF.

The following guidelines of relatedness are used modified from the NIH guidelines:

**Related:** The adverse event is related to the FMT material – i.e. an event that follows a reasonable temporal sequence from administration of the FMT material, follows a known or expected response pattern to the FMT material, that is confirmed by improvement on stopping and reappearance of the event

on repeated exposure and that could not be reasonably explained by the known characteristics of the patient's clinical state.

**Not Related:** The adverse event is not related to the FMT material - i.e. another cause of the event is most plausible; and/or a clinically plausible temporal sequence is inconsistent with the onset of the event and the study intervention and/or a causal relationship is considered biologically implausible.

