#### 5.4. Summary of Clinical Data

FMT-instillation of stool from a healthy donor into the intestine of a CDI patient has been shown to be an effective approach for the treatment of recurrent CDI. A recent randomized controlled trial of FMT in patients with recurrent CDI found a 90% success rate. Its efficacy is thought to be due to restoration of gut microbial diversity and colonization resistance. In mouse models of CDI recurrence, FMT has been shown to be highly effective at reestablishing colonization resistance to *C. difficile* by restoring bacterial community structure in the gut. Current guidelines recommend that FMT be reserved for patients who have had several episodes of recurrent CDI and have exhausted other treatment options. Because of the high risk of recurrence with antibiotic use and lack of effective therapies available, novel and innovative approaches to prevent CDI recurrence in hospitalized patients receiving antibiotics would be a major advance in the field. This is a critical gap that our research group strives to fill.

Restoration of gut microbiota and prevention of antibiotic-associated diarrhea and CDI has been studied in several clinical trials using concurrent probiotics with antibiotic therapy with conflicting, although largely positive results. Given that FMT is comprised of entire bacterial communities rather than isolated taxa, FMT offers an ecological advantage. FMT, has been shown to be a highly effective and safe intervention for treatment of recurrent CDI. A recent systematic review and pooled analysis reports FMT was 83% effective in the treatment of recurrent CDI, with few reported adverse events. Although not fully elucidated, the hypothesized mechanism of FMT for CDI is that normal colonic microbiota outcompete and competitively exclude *C. difficile*.

Recently, Osman et al presented effectiveness and safety data from a 2,050 patient cohort among OpenBiome recipients. The data suggests that among the 42 suspected adverse events, 0 were definitely related to FMT material based on NIH criteria after a comprehensive investigation (Appendix 16.1).

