### **5.6.1. Known Potential Risks**

In the first randomized controlled trial on FMT, mild diarrhea (94%), abdominal cramping (31%) and belching (19%) were observed on the day of colonoscopic infusion; however, these symptoms resolved within 3 hours. Of note, in follow-up, three patients who were treated with donor feces (19%) had constipation. No other adverse events related to the study treatment were reported.

There is a paucity of data on long term follow-up related to FMT. Brandt et al. conducted a retrospective multi-center study (n=77) with a follow up varying between 3 to 68 months and reported 7 deaths. However, none were related to FMT. A recent systematic review on the safety of FMT suggests there are risks including: infection (fever, bacteremia), autoimmune disease (peripheral neuropathy, Sjogren's syndrome, idiopathic thrombocytopenic purpura and rheumatoid arthritis, inflammatory bowel disease flare among patients with ulcerative colitis) and other studies have suggested a link to metabolic syndrome. However, comprehensive screening of donors should decrease any potential future risk. OpenBiome donors are highly selected with only 2.8% of candidate donors qualifying to donate after screening both infectious disease and microbiome-mediated disease (Appendix 16.3).

While there is the potential for additional risks associated with FMT treatment due to the nature of capsules, OpenBiome donors are highly screened before selection to ensure safety. OpenBiome donors undergo a rigorous clinical evaluation with an internal medicine specialist as well as a wide range of screenings for infectious pathogens.

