patient's antibiotic treatment plus seven days post-antibiotic treatment.

**Group 2:** This group will receive 30 oral FMT capsules one time 48-72 hours following completion of antibiotic treatment.

**Oral FMT capsules:** Capsules contain fecal microbiota sourced from healthy donors and screened for pathogens.

**Control:** The control is an oral placebo capsule identical to the FMT capsules given to the intervention groups and will be provided by OpenBiome. The placebo capsule consists of glycerol and saline and will be administered daily as five capsules per day during the duration of antibiotic treatment plus an additional seven days post-antibiotic treatment (group 3). Patients will be fasting (clear liquids allowed) for at least 2 hours prior to administration and at a minimum of 1-hr post-administration (Appendix 17.1)

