## **9.8. Modification of Study Intervention/Investigational Product for a Participant**

If the participant is unable to complete the full dose of DE or placebo in one sitting the actual dose ingested will be recorded. Further study product administration, including the remainder of the incomplete dose and scheduled upcoming doses as applicable will be at the discretion of the treating physician. The remaining capsules scheduled to be administered may be offered to the participant on the same day they were scheduled. Intention-to-treat analysis will be utilized according to best practices in clinical trials.

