### 17.3. NIH Common Terminology Criteria for Adverse Events (CTCAE)

#### Adverse Events Recording Form

Record of adverse events:				
System:	Present	Grade	Attribute	Describe reaction (refer to appendix 9)
Systemic				
Infection				
Injection site reaction				
Skin/dermatologic				
Cardiovascular				
Gastrointestinal				
Neurologic				
Respiratory				
Musculoskeletal				
Genitourinary				
Ocular/Visual				
Endocrine/metabolic				
Laboratory AE:				
Hematologic				
Chemistry				
Urinalysis				

NIH Adverse Event Severity Grading Scale*	
Scale	Description
1	Mild      Symptoms causing no or minimal interference with usual social and functional activities
2	Moderate      Symptoms causing greater than minimal interference with usual social and functional activities
3	Severe      Symptoms causing inability to perform usual social and functional activities
4	Potentially life-threatening      Symptoms causing inability to perform basic self-care functions OR medical and operative intervention indicated to prevent permanent impairment, persistent disability, or death
5	Death      Fatal event related to adverse event

NIH Adverse Event Relatedness *	
Likely	Description
Definitely related	The adverse event is related to the FMT material – i.e. an event that follows a reasonable temporal sequence from administration of the FMT material, follows a known or expected response pattern to the FMT material, that is confirmed by improvement on stopping and reappearance of the event on repeated exposure and that could not be reasonably explained by the known characteristics of the patient's clinical state.
Not related	The adverse event is not related to the FMT material. - i.e. another cause of the event is most plausible; and/or a clinically plausible temporal sequence is inconsistent with the onset of the event and the study intervention and/or a causal relationship is considered biologically implausible.

\*Source: NIH Adverse Event and Serious Adverse Event Guidelines, available online at  
[https://www.nia.nih.gov/sites/default/files/niaaeandsaeguidelinesfinal011012\\_0.doc](https://www.nia.nih.gov/sites/default/files/niaaeandsaeguidelinesfinal011012_0.doc)

Completed \_\_\_\_\_

Date \_\_\_\_\_

Name \_\_\_\_\_

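### The definition of 'Related' in 13.2.2 requires reappearance on re-exposure, so no event after a completed Group 2 single dose can meet it, and 13.5.1 and 13.5.2 do not say whether they use it

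*Combined protocol and SAP*

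**What the plan says.** Section 13.2.2 introduces its categories with "The following guidelines of relatedness are used modified from the NIH guidelines" and gives two levels.

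- **'Related'** is one sentence of joined conditions. The event must follow reasonable timing; it must be one that "follows a known or expected response pattern to the FMT material, that is confirmed by improvement on stopping and reappearance of the event" when dosing is repeated; and it must not be reasonably explained by the patient's clinical state.
- **'Not Related'** has its own grounds: "another cause of the event is most plausible; and/or a clinically plausible temporal sequence is inconsistent with the onset of the event", or a causal link that is biologically implausible.

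The form in 17.3 carries the same text ("that is confirmed by improvement on stopping and reappearance of the event on repeated exposure and that could not be reasonably explained") but labels the level 'Definitely related'. Section 13.3.2 uses that label too. Coding is not optional: 13.1.1 requires every AE to be graded for relationship, 13.2.2 asks for relatedness to be evaluated for all AEs, and causality is a CRF field in 13.3.1.

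On exposure, 7.1 says of Group 2: "This group will receive 30 oral FMT capsules one time 48-72 hours following completion of antibiotic treatment". For a dose not finished in one sitting, 9.8 adds: "The remaining capsules scheduled to be administered may be offered to the participant on the same day they were scheduled".

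Section 13.5.1 suspends enrolment and dosing on any of three triggers: (1) three or more participants in a group with a Grade 3 AE of the same organ system deemed related; (2) any related SAE, including donor-to-recipient transmission of a pathogen; (3) a pattern that the Medical Monitor considers related. Section 13.5.2 uses a related severe or serious AE as an individual criterion. Neither section cites 13.2.2.

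**The concern.** Improvement on stopping and reappearance on re-exposure can be observed only when dosing is repeated and the event is reversible. One of the two FMT arms has a single dose, and some of the most serious outcomes are not reversible. For those cases an assessor who follows the text cannot record 'Related', and may have no ground for 'Not Related'. The assessor must then depart from the definition or leave a mandatory field unresolved, and different assessors may do so differently. Because 13.5.1 turns on the word 'related', it also matters whether it borrows this definition.

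**Working it through.** The plan gives no figure for relatedness or for how often the halting rules would act, so there is nothing to reproduce. The check sets the required elements against each exposure pattern.

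| Situation | Improvement on stopping | Reappearance on re-exposure | Can meet 'Related' literally? |
|---|---|---|---|
| Group 2, dose completed (7.1, 11.2) | Nothing left to stop | No second dose | No |
| Group 2, dose interrupted, rest taken same day (9.8) | Possible | Possible | In principle |
| Group 1, reversible event, dosing interrupted and resumed | Possible | Possible | In principle |
| Group 1, dosing ended for good because of the event (13.3.2 allows this for an intolerable SAE) | Possible | No | No, unless it had already recurred on an earlier dose |
| FMT arms, event starts after the last capsule | No | No | No |
| Fatal event, no earlier episode | No | No | No |
| Fatal event in a daily arm, after an episode that resolved and recurred on a later dose | Seen in the earlier episode | Seen in the recurrence | Arguably |

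Section 8.4.2.2, on antibiotic courses beyond 14 days, uses group numbers that do not match 7.1. Those passages must be reconciled, but on neither reading does Group 2 receive a second 30-capsule dose.

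**Size.** Group 2's share of planned FMT patients is 10/(10 + 10) = 10/20, or half. Among completed doses there, the number of events able to meet the literal text is 0.

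**Are the levels exhaustive?** Take a plausible, well-timed event after a completed Group 2 dose, with no better explanation. It fails 'Related' for lack of re-exposure. It also fails 'Not Related', because no other cause is most plausible, the timing fits and the link is not implausible. It has no level.

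**The known-or-expected condition.** Section 13.3.2 provides for suspected *unexpected* serious reactions, which this condition would keep out of 'Related'. Its reach is limited: 5.6.1 lists known reactions (for example "mild diarrhea (94%), abdominal cramping (31%) and belching (19%) were observed on the day of colonoscopic infusion") as well as infection and autoimmune disease, and 13.2.3 lists solicited symptoms.

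**Consequence for 13.5.1, if 13.2.2 governs it.** For completed Group 2 doses, trigger 1 cannot fire at any true event rate. Nor can trigger 2, apart from the transmission it names. For contrast, suppose relatedness could be judged without re-exposure and all 10 patients were dosed. With an assumed per-patient rate p, which the documents do not give, trigger 1 has probability P(X ≥ 3) = 1 − Σ C(10,k) p^k (1−p)^(10−k), summed over k = 0 to 2. This is 0.070 at p = 10%, 0.322 at 20% and 0.617 at 30%.

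**The case against.** The strongest reply is that 13.5.1 does not import the literal test. Trigger 2 counts donor-to-recipient transmission as related, which re-exposure would not ordinarily establish. Section 5.6.2 attributes infection to FMT by culture and strain-typing. Section 13.5.1 speaks of events deemed or considered related, and 13.2.2 calls its own text guidelines. This stands as a sign of intent. A reader might infer from the definition that the halting rules are switched off for Group 2; the documents do not support that as fact. They also do not state which standard applies.

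A second reply is that nothing escapes review, and this stands in full. Under 13.3.2 every SAE is reviewed whatever its cause, each SAE report must comment on possible causation, and certain deaths go to the DMC if they could be related. Trigger 3 rests on the Medical Monitor's judgement. The PI can halt (8.6.1) and the DMC can recommend suspension (13.6). The outcomes in 7.2.3 are all-cause, so no planned safety proportion changes. A reader who inferred missed events or biased safety results would be going beyond the text.

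A third reply is that a death in a daily arm could follow an episode that resolved and recurred. That is right, so it would be too strong to say that no fatal event can ever qualify.

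A reader might also try to size the problem from 5.4, where "among the 42 suspected adverse events, 0 were definitely related to FMT material based on NIH criteria after a comprehensive investigation". That cohort received liquid preparations, and nothing shows that it used this definition, which 13.2.2 describes as modified. It does not measure this defect.

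Finally, 13.3.2 points to Appendix II for SUSARs, which may mean the 17.4 flow chart. Its content is not visible, and neither are the MOP or the DMC charter; any of them may supply a standard.

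**Conclusion.** The defect in 13.2.2 and 17.3 is real on a literal reading. 'Related' cannot be reached after a completed Group 2 dose (half of the planned FMT patients), for an event that starts after the last capsule, or for a fatal event without an earlier episode that resolved and recurred. With only two levels, a plausible event may fit neither, although coding is mandatory. Nothing in the visible text marks the re-exposure condition as optional.

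The effect on halting is conditional. If 13.2.2 governs 13.5.1, trigger 1, and trigger 2 apart from transmission, cannot fire for completed Group 2 doses. If it does not, those triggers have no stated general causality standard in the visible text, only the one for infection in 5.6.2. The wording leans towards the second reading. Either way, what is at risk is consistent causality coding and clarity about automatic suspension, not detection or review. It should be fixed.

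**What to change.** In 13.2.2 and 17.3:

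1. Make improvement on stopping and reappearance on re-exposure supportive evidence where they can be observed, not requirements.
2. Do not require a known or expected pattern.
3. Word the two levels so that every event falls in one of them. A 'possibly related' level is an option, not a necessity.

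Use one label throughout, including the list in 13.3.2, and align the 17.4 flow chart if it carries causality steps. State in 13.5.1 and 13.5.2 which causality category applies. The halting threshold is for the sponsor and the DMC to decide.

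The drafting cost is small: a wording amendment, a cross-reference in two sections and one AE form field. The real cost is that more events may be coded 'Related', and one related SAE suspends enrolment and dosing under trigger 2. As an illustration, at assumed per-patient rates of 5% and 10%, the chance of at least one such SAE in 10 patients is 1 − 0.95^10 = 0.401 and 1 − 0.90^10 = 0.651. That compares with 0 for completed Group 2 doses, transmission aside, if the present literal text governs. If 13.5.1 already works on a broader meaning, the change in practice is smaller.

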### 13.2.3. *Solicited Adverse Events after FMT*

In addition to open-ended questions on adverse events meeting the above definitions, specific potential adverse events will be inquired about during the follow up period (following intervention through to 6 months after randomization):

Symptom that is clinically more severe than participant's baseline	Severity				
	Grade 1	Grade 2	Grade 3	Grade 4	Grade 5
Fever*	38.0 - 39.0 degrees C (100.4 - 102.2 degrees F)	>39.0 - 40.0 degrees C (102.3 - 104.0 degrees F)	>40.0 degrees C (>104.0 degrees F) for <=24 hrs	>40.0 degrees C (>104.0 degrees F) for >24 hrs	Death
Diarrhea	Increase of <4 stools per day over baseline pre-FMT; mild increase in ostomy output compared to baseline	Increase of 4 - 6 stools per day over baseline; moderate increase in ostomy output compared to baseline; limiting instrumental ADL	Increase of >=7 stools per day over baseline; incontinence; hospitalization indicated; severe increase in ostomy output compared to baseline; limiting self-care ADL	Life-threatening consequences; urgent intervention indicated	Death
Vomiting	1 - 2 episodes (separated by 5 minutes) in 24 hrs	3 - 5 episodes (separated by 5 minutes) in 24 hrs	>=6 episodes (separated by 5 minutes) in 24 hrs; tube feeding, TPN or hospitalization indicated	Life-threatening consequences; urgent intervention indicated	Death
Abdominal Pain	Mild pain	Moderate pain; limiting instrumental activities of daily life	Severe pain; limiting self-care activities of daily life	n/a	n/a
Bloating	No change in bowel function or oral intake	Systemic, decreased oral intake; change in bowel function	n/a	n/a	n/a

Symptom that is clinically more severe than participant's baseline	Severity				
	Grade 1	Grade 2	Grade 3	Grade 4	Grade 5
Constipation	Occasional or intermittent symptoms; occasional use of stool softeners, laxatives, dietary modification, or enema	Persistent symptoms with regular use of laxatives or enemas indicated; limiting instrumental activities of daily life	Symptoms interfering with self-care activities of daily life; obstipation with manual evacuation indicated	Life-threatening consequences (e.g. obstruction, toxic megacolon); urgent intervention indicated	Death

